All of these abbreviations may or may not be used in protocol.

PROTOCOL SIGNATURE

I confirm that I have read this protocol, and I will conduct the study as outlined herein and according to the ethical principles stated in the latest version of the Declaration of Helsinki, the applicable ICH guidelines for good clinical practice, and the applicable laws and regulations of the federal government.

I will provide copies of the protocol and all pertinent information to all individuals responsible to me who assist in the conduct of this study. I will discuss this material with them to ensure that they are fully informed regarding the study treatment, the conduct of the study, and the obligations of confidentiality.

Signature of Principal Investigator

12/3/2019 Date

[name] PhD, MAcOM, LAc Principal Investigator Name

College of Nursing, University of Utah Name of Institution

STUDY SUMMARY

Title	Acupuncture Treatment of Chemotherapy-
	Induced Peripheral Neuropathy (CIPN) in
	Women with Breast or Gynecologic
	Cancers: Feasibility and Mechanisms of
	Action
Short Title	CIPN Acu
Protocol Number	N/A
Phase	Clinical study phase: pilot phase II study
Design	Single arm, pilot feasibility study
Study Duration	18 months
Study Center(s)	Single-center: HCI/HCH
Objectives	This pilot study aims to demonstrate
	feasibility to recruit, retain and provide the
	study intervention and to identify potential
	mechanisms of action of acupuncture in
	CIPN management.
Number of Subjects	N=20
Diagnosis and Main Eligibility Criteria	This study will enroll female patients who
	have completed paclitaxel or docetaxel
	treatment at least 3 months prior with at
	least one month of altered sensation in feet
	(with or without presence in one or both
	hands) and/or pain with a score of greater
	than or equal to 20 for CIPN on the
	sensory subscale of the CIPN-20.
	Enrollment will be limited to patients with
	breast, ovarian, cervical, endometrial, or
	uterine cancer with CIPN and completed
	paclitaxel or docetaxel treatments.
Statistical Methodology	Primary Endpoints: Mean monthly
	enrollment, percentage completion rate of
	all study procedures, frequency count of
	serious adverse events, and percentage of
	enrolled participants completing
	questionnaires will be calculated. Data
	will be collected via REDCap and
	analyzed with SPSS.
	Analysis of demographic data will consist
	of calculating means standard deviations
	frequencies and proportions. Analysis of
	feasibility data will consist of calculating
	frequencies and percentages Analysis of
	questionnaires will consist of within-

group pre/post analysis with student t-test and chi square with significance will be set at .05 and two-tailed hypotheses.
Sample Size Estimation: A sample size of 25-30 participants is ideal for a pilot feasibility study ¹ . However, we are recruiting only 20 participants due to funding constraints.

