1.2 Secondary Objectives and Endpoints

To evaluate the impact of AT on the reported experience of CIPN.

- 1.2.1 To evaluate central pain processing and cortical connectivity in patients with CIPN treated by acupuncture by analyzing fMRI of all participants.
- 1.2.2 To evaluate if there is any change in patient-reported measures from before AT to after study completion.

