5.1 Inclusion Criteria Yes/No (Response of "no" = patient ineligible)

- 5.1.1 _____ Female age 18 or older.
- 5.1.2 Histologically proven breast, uterine, cervical or ovarian cancer of any stage.
- 5.1.3 Received either (1) a Paclitaxel treatment dose of at least 480 mg/m² paclitaxel as a single or combination agent or (2) a Docetaxel treatment dose of at least 150 mg/m² docetaxel as a single or combination agent. Treatment must be completed at least 3 months prior to enrollment.
- 5.1.4 Eligible patients report at least 1 month of altered sensation and/or pain in the feet (with or without presence in one or both hands) with a score of greater than or equal to 20 for CIPN on the sensory subscale of the CIPN-20 (scale 0-100).

5.1.5. _____ Able to provide informed consent and willing to sign an approved consent form that conforms to federal and institutional guidelines.

5.1.6. ECOG status of 0 (asymptomatic), 1 (symptomatic but completely ambulatory) or 2 (symptomatic, <50% in bed during the day).

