6 STRATIFICATION FACTORS N/A

7 TREATMENT PLAN

7.1 Administration Schedule

Twenty participants will be enrolled. The manualized acupuncture treatment (AT) intervention will be designed by [name] and [name] and administered by [name] and members of Huntsman acupuncture team. Ten sessions of AT will be delivered: twice per week for 2 weeks, thereafter once per week for six weeks, with a total of 10 treatments during a two-month course. Each session will last 45-60 minutes, with acupuncture needles retained 30-40 minutes. A minimum of 8 treatments must be received within the acupuncture treatment window. Concurrent medications are allowed as prescribed and will be tracked in the study and analyzed as potential confounders.

Participants in the study will undergo study interview and fMRI at the following two time points: within 9 days after baseline following enrollment and within one week of acupuncture treatment completion. Clinical data including current medications and medical history and fall rates will be gathered during the baseline and study conclusion. Questionnaires will be completed in person or emailed to patients via REDCap at baseline and study conclusion, as well as at a 3-month follow-up. Reminder calls and AT appointments will be scheduled by HCI Wellness and Integrative Health Center personnel in coordination with the study coordinator (SC). The SC will aid participants in scheduling fMRI with an online scheduling system.

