9 STUDY CALENDAR

			W	eek	(+/·	- 2 d	lays	5)			Week (+/- 7 days)		
Examination	Screenin g ¹	Baseline ^{1,} 2 Day 1	1	2	3	4	5	6	7	8	9	End of study ⁵	22
Informed consent	Χ												
Eligibility criteria	X												
Concomitant medications	X											X	
Questionnaires ³													
• CIPN-20	X											X	X
• BPI		X										X	X
CIPN-R-ODS		X										X	X
• MAIA-2		X										X	X
• Demographics		X											
Acupuncture treatment (AT) ⁴				X X	X X	X	X	X	X	X	X		
fMRI ⁶			X									X	

¹ Screening visit and Baseline visit can occur on the same day.

- ² Day 1 (Baseline) should occur within 2 weeks of the screening visit.
- ³ Questionnaires include: (See Appendices).
- ⁴ Acupuncture treatment (AT) will occur at the Wellness & Integrative Health Center at HCI. Twice a week treatments will occur within 4 business days.
- ⁵ End of study visit should occur within one week of final acupuncture treatment.
- ⁶ Must be within 9 days of baseline visit. If participant prefers, first study fMRI can be same day as first AT treatment.

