10 STUDY PROCEDURES

This study will enroll female patients who have completed treatment with either paclitaxel or docetaxel at least three months prior. Paclitaxel is a neurotoxic chemotherapy known to cause CIPN. Docetaxel is also a neurotoxic chemotherapy known to cause CIPN. Patients must have experienced at least one month of altered sensation in feet (with or without

presence in one or both hands) and/or pain with a score of greater than or equal to 20 for CIPN on the sensory subscale of the CIPN-20. We will commence recruitment 3 months after patients have completed their last chemotherapy dose.

Patients will be recruited from the Huntsman Cancer Center Oncology Clinics in collaboration with their oncologists.

For this study, enrollment will be limited to patients with breast, ovarian, cervical, endometrial, or uterine cancer with CIPN and completed chemotherapy treatments.

Visits:

Screening Visit:

Potentially eligible subjects will be scheduled for a screening visit. After informed consent is obtained, the SC will review and confirm inclusion/exclusion criteria. The SC will take a brief medical, history and administer the CIPN-20 questionnaire. If all inclusion and exclusion criteria are fulfilled, the subject will be scheduled for a baseline visit. This visit may occur on the same day as screening, but must occur within 2 weeks of study screening visit. If the participant has received treatment outside of University of Utah Health a medical record release form will be initiated and submitted as appropriate.

Baseline Visit:

Patients diagnosed with breast, ovarian, cervical, endometrial, or uterine cancer who will be treated with paclitaxel or docetaxel chemotherapy associated with CIPN will undergo a number of questionnaires. The patient will then be enrolled in the study and scheduled in the Wellness Center for acupuncture therapy (AT). All participants will be scheduled for fMRI, which must occur within nine days after baseline.

Participants will undergo study interview and fMRI within 9 days after baseline following enrollment.

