Clinical data including current medications and medical history and fall rates will be gathered. Questionnaires (BPI, CIPN-20, CIPN-R-ODS, MAIA-2, Demograhpics) will be completed in person or emailed to patients via REDCap. Reminder calls and AT appointments will be scheduled by HCI Wellness and Integrative Health Center personnel in conjunction with a SC. The SC will aid participants in scheduling fMRI appointments online. AT treatments will occur within 7 days/4 business days in general. If participant prefers the first study fMRI and first AT appointment can occur same day, with the fMRI procedure occurring prior to AT treatment.

Follow up Visits:

Participants will receive 10 sessions of AT: twice per week for 2 weeks, thereafter once per week for six weeks, with a total of 10 treatments during a two-month course. Each session will last 45-60 minutes, with acupuncture needles retained 30-40 minutes. A minimum of 8 treatments must be received by each participant with no more than 9 days' gap between weekly treatments permitted (sessions 5-10). Concurrent medications are allowed as prescribed and will be tracked in the study and analyzed as potential confounders.

Final Visit:

Participants will undergo examination within one week of AT completion. This will include the fMRI scan and questionnaires. Compensation for participation will be offered at this visit.

Procedures:

Measures: Questionnaires will be completed in person or emailed to patients via REDCap at baseline and study conclusion, as well as at a 3-month follow-up. *Primary Endpoints:* Mean enrollment, percentage completion rate of all study procedures, frequency count of serious adverse events, and percentage of enrolled participants completing questionnaires will be calculated. Data will be collected via REDCap, stored in the Research Subject Registry (RSR) and analyzed with SPSS.

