12 STATISTICAL CONSIDERATIONS

Data will be collected via REDCap and analyzed with SPSS. Missing data will be handled with imputation of the median value of all available data for each individual item.¹⁹

Demographics: Analysis of demographic data will consist of calculating means, standard deviations, frequencies, and proportions. Demographic information to include: age, marital status, race and ethnicity, current medications and medical history.

Feasibility data: will be analyzed by calculating frequency and percentages, specifically:

- **Recruitment** frequency count (enrollment of 20 women, average of 2 eligible women per month to participate in the trial, identification of appropriate recruitment strategies, the appropriateness of eligibility criteria),
- **Retention** frequency and percentage (70% or more participants comply with 8 or more AT sessions and complete both fMRI scans)
- Safety frequency count (zero serious adverse events directly related to AT)
- **Questionnaire completion** frequency and percentage (70% or more enrolled participants complete at least 80% of questions at all protocol-directed time points).

Questionnaires: analyses will consist of student t-test and chi square computations according to the type of data.

- CIPN-20
- CIPN-R-ODS
- BPI
- Multidimensional Assessment of Interoceptive Awareness (MAIA-2)

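### The pre/post questionnaire analysis in a single arm names an unqualified chi-square and no matched test

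*Combined protocol and SAP*

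**What the plan says.** The study has one arm of 20 women, a number set by budget (Study Summary; Section 4.3). Secondary objective 1.2.2 is about change in the same women: "To evaluate if there is any change in patient-reported measures from before AT to after study completion".

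The Statistical Methodology entry of the Study Summary describes the questionnaire analysis as within-group: "group pre/post analysis with student t-test and chi square with significance will be set at .05 and two-tailed hypotheses". Section 12, under Questionnaires, says that "analyses will consist of student t-test and chi square computations according to the type of data" and then lists CIPN-20, CIPN-R-ODS, BPI and MAIA-2. It does not repeat that the comparison is within-group, and it does not say which variable goes to which test.

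No section uses the terms paired, matched or McNemar for any test. The appendices rate the instruments numerically: CIPN-20 items 1 to 4, CIPN-R-ODS items 0 to 5, BPI items 0 to 10 plus one relief item in percent, and MAIA-2 items 0 to 5. No responder status or cut-point is defined for analysis. The CIPN-20 sensory score of 20 in Section 5.1 is an eligibility threshold.

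**The concern.** With one arm there is no between-group table. A chi-square on questionnaire data for objective 1.2.2 would therefore be computed on two measurements of the same women, but Pearson's test assumes independent observations. It could be set up in two ways, and neither answers the objective properly:

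- **Time by status** (before and after as two rows of 20). This uses only the two totals and discards which women changed.
- **Before by after** (each woman counted once). The observations are independent, but the test asks whether the earlier status predicts the later one. It can be significant with no net change.

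At stake is the p-value for any questionnaire variable that is turned into categories.

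**Working it through.** The plan gives no figure to reproduce: there is no power calculation, effect size, SD or pre/post correlation. From the documents come n = 20, two-sided .05, and 14 women as 70% of 20 (the retention target in Section 12). Everything else below is assumed for illustration.

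**1. Formulas.** Take n pairs, with b women improving (positive to negative), c worsening, and p the mean of the before and after proportions.

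- Time-by-status chi-square = (b − c)² / [2n p(1 − p)]
- Uncorrected McNemar = (b − c)² / (b + c)

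The numerators are equal. Chi-square therefore gives the larger p-value when b + c is below 2n p(1 − p), and the smaller one when it is above.

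**2. Assumed table: 14/20 before, 8/20 after.** Here p = 22/40 = 0.55, 2n p(1 − p) = 40 × 0.55 × 0.45 = 9.9, and (b − c)² = 36. Chi-square is 36/9.9 = 3.64 in every row.

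| Improve, worsen | Chi-square p | McNemar statistic | McNemar p | Exact McNemar p |
|---|---|---|---|---|
| 6, 0 | 0.057 | 36/6 = 6.0 | 0.014 | 0.031 |
| 7, 1 | 0.057 | 36/8 = 4.5 | 0.034 | 0.070 |
| 10, 4 | 0.057 | 36/14 = 2.57 | 0.109 | 0.180 |

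The chi-square p-value can err in either direction.

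**3. Assumed cross-table with no net change.** Eight women are positive both times, 8 negative both times, 2 improve and 2 worsen, so 10 of 20 are positive each time. Chi-square = 20 × (8 × 8 − 2 × 2)² / (10 × 10 × 10 × 10) = 7.2, p = 0.007. McNemar = 0/4 = 0, p = 1.

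**4. Behaviour over repeated trials.** Assume bivariate normal scores with pre/post correlation r, split at the baseline population median. With no change, the chance of being above it both times is 1/4 + arcsin(r)/(2π). The rejection rates below come from enumerating all paired tables. Percentages are for r = 0.3 / 0.5 / 0.7.

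| Test | No change, n = 20 | No change, n = 14 | Power for 0.5 SD shift, n = 20 |
|---|---|---|---|
| Time by status | 2.5 / 1.4 / 0.6 | 2.4 / 1.4 / 0.6 | 20 / 18 / 16 |
| Before-by-after cross-table | 14 / 31 / 61 | 12 / 25 / 49 | not a test of change |
| Exact McNemar | 1.9 / 1.5 / 0.9 | 1.2 / 0.7 / 0.3 | about 16 / 17 / 18 |
| Mid-p McNemar | 3.9 / 3.5 / 2.6 | 3.1 / 2.3 / 1.3 | 23 / 26 / 29 |
| Uncorrected McNemar | about 4.3 / 4.6 / 5.0 | about 5.0 / 5.0 / 4.1 | 24 / 28 / 36 |

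The paired t-test on the undivided score has power 43 / 56 / 78 at n = 20 for the same shift. At n = 14, power is about 8 / 7 / 6 for exact McNemar and 14 / 12 / 10 for time by status.

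**The case against.** The Summary says only chi square, within a phrase about within-group pre/post comparison, and McNemar's statistic is itself referred to a chi-square distribution. The same phrase implies a paired t-test, so a consistent reader could take both tests as matched. All four instruments are scored numerically and Section 12 assigns tests by data type, so the scale scores would go to the t-test and chi-square might never be used. The tables and correlations above are assumed. The more natural misuse, time by status, is conservative when nothing changes. The standard replacement gains little in its exact form: at n = 14 it has less power than the test criticised.

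Most of this stands. A reader might infer that an ordinary Pearson test is definitely planned, that the t-test is unpaired, or that false-positive findings will result. The documents support none of these: the form of chi-square is unstated, the within-group wording points to pairing, and inflated rejection appears only with the cross-table, on assumed correlations.

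The objection does not remove the gap. Section 12, the statistical section proper, drops the within-group wording, and nowhere is a matched test named or a use for chi-square defined. The variable, the cut-point and the form of test are left to be chosen after the data are seen.

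**Conclusion.** The point holds as a minor one. The plan names an unqualified chi-square for repeated measurements in one arm. If a questionnaire variable is made categorical and the wording is followed literally, the p-value is miscalibrated or answers a different question. In the assumed 14/20 to 8/20 table it stays at 0.057 while uncorrected McNemar ranges from 0.014 to 0.109. The size depends on assumed tables, correlations and shift, and the condition may never be met, because no categorical questionnaire variable is defined.

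Only secondary objective 1.2.2 is touched. A reader might extend the criticism to the trial's main conclusions or its sample size. The documents do not support that: the primary feasibility endpoints are counts and percentages, and N = 20 is set by budget. Which visit supplies the pre-treatment CIPN-20 score, and how the 3-month questionnaires are used, are separate matters and add no weight here.

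**What to change.** In the Study Summary and Section 12, state that each questionnaire scale score is compared before and after AT by paired t-test, reporting mean change with its 95% CI. Delete chi-square for pre/post comparisons.

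If a binary status is wanted, define it in advance. Analyse it by McNemar's test, with the paired difference in proportions and its 95% CI, and state the version. In the cases worked here the exact test is conservative at 14 to 20 women. The uncorrected version is closest to 5%, but it relies on a large-sample approximation with few discordant pairs. Mid-p lies between the two.

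The cost is two or three sentences and no new data, plus a check of which McNemar version the SPSS procedure reports. The downside is that a binary result has low power at this size (about 16% to 36% across McNemar versions for an assumed 0.5 SD shift at n = 20), so it can only be supportive.

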1 OBJECTIVES

This pilot study aims to evaluate the feasibility to conduct a study of acupuncture treatment (AT) for Chemotherapy-Induced Peripheral Neuropathy (CIPN) at Huntsman Cancer Institute and to investigate changes in physiological biomarkers when using acupuncture to treat CIPN.

1.1 **Primary Objectives and Endpoints**

To evaluate the feasibility to conduct a trial of AT for CIPN + standard of care therapy. Primary feasibility objectives will be evaluated in terms of recruitment (enrollment of 20 women, average of 2 eligible women per month to participate in the trial, identification of appropriate recruitment strategies, the appropriateness of eligibility criteria), retention (70% or more participants comply with 8 or more AT sessions and complete both fMRI scans), safety (zero serious adverse events directly related to AT) and questionnaire completion (70% or more enrolled participants comply with all data collection).

1.1.1 Primary outcome measures: Mean enrollment, completion rate of AT, fMRI, rate of serious adverse events, rate of questionnaire completion.

1.2 Secondary Objectives and Endpoints

To evaluate the impact of AT on the reported experience of CIPN.

- 1.2.1 To evaluate central pain processing and cortical connectivity in patients with CIPN treated by acupuncture by analyzing fMRI of all participants.
- 1.2.2 To evaluate if there is any change in patient-reported measures from before AT to after study completion.

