2 BACKGROUND

Chemotherapy-induced peripheral neuropathy (CIPN) is one of the most common and disabling complications of cancer chemotherapy. CIPN is a major cause of morbidity and reduced quality of life among cancer survivors due to pain, gait instability, and fall related injury. Up to 60% of patients receiving potentially neurotoxic chemotherapeutics develop CIPN, 40% of whom have persistent neuropathy after termination of chemotherapy.^{2,3} CIPN commonly necessitates dose reduction or cessation of therapy, potentially limiting treatment efficacy and likely impacting patient outcomes.⁴ First-line treatments include anticonvulsants, tricyclic antidepressants, selective serotonin and norepinephrine reuptake inhibitors (SSNRIs) and topical lidocaine.⁵

Second-line treatments include opioids. Given the risk of abuse, overdose and addiction, treatments besides opioids are advised and warrant investigation. A multimodal approach may be most effective, with acupuncture being a safe option reporting low rates of adverse events⁶. Acupuncture treatment (AT) is a well-tolerated and safe treatment option frequently used for symptoms associated with cancer therapies such as nausea, vomiting, xerostomia and fatigue.⁷ Several case series and small uncontrolled trials of AT for CIPN suggest potential efficacy, although well-designed and powered clinical trials are lacking and mechanisms underlying AT's potential efficacy are unknown.⁸⁻¹⁴

Although drug-induced damage to the peripheral nervous system is well recognized in CIPN, the central nervous system (CNS) also shows concomitant involvement. Much of our current understanding of the pathophysiology of central pain processing in chronic painful conditions such as diabetic neuropathy, trigeminal neuralgia, post-herpetic neuralgia and chronic low back pain has utilized functional magnetic resonance imaging (fMRI). Previous pain-related functional studies identified alterations in brain activation in multiple cortical and subcortical regions including the frontal lobe, insular cortex, somatosensory cortex, thalamus, periaqueductal grey and precuneus.¹⁵

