4.3 Number of Patients

Twenty participants will be enrolled. Sample size for this pilot feasibility study is determined by budgetary constraints. While a sample of 25-30 would be ideal for the aims of this study¹, we are limited by our study budget to twenty participants.

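### The secondary objective is worded as the impact of AT, but a single-arm pre/post test can only describe change, and the 'before' CIPN-20 value may be the score that selected the women

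*Combined protocol and SAP*

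**What the plan says.** The Study Summary gives the design as "Single arm, pilot feasibility study". The lead sentence of Section 1.2 is "To evaluate the impact of AT on the reported experience of CIPN". Item 1.2.2 beneath it is narrower: "To evaluate if there is any change in patient-reported measures from before AT to after study completion".

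The Study Summary (Statistical Methodology) plans a within-"group pre/post analysis with student t-test and chi square with significance will be set at .05 and two-tailed hypotheses". Section 12 repeats the t-test and chi-square for four questionnaires (CIPN-20, CIPN-R-ODS, BPI, MAIA-2). It gives no significance level, lead scale or multiplicity rule, and does not say how change will be interpreted. On the number of women, Section 4.3 says "Sample size for this pilot feasibility study is determined by budgetary constraints".

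Section 5.1.4 admits women "with a score of greater than or equal to 20 for CIPN on the sensory subscale of the CIPN-20 (scale 0-100"). CIPN-20 is also an outcome. The Section 9 calendar marks it at screening, end of study and week 22, but not at baseline, where the other three questionnaires are marked. Section 10 also gives it at screening, yet under the Baseline Visit says "Questionnaires (BPI, CIPN-20, CIPN-R-ODS, MAIA-2, Demograhpics) will be completed in person or emailed to patients via REDCap". Calendar footnote 1 allows screening and baseline on the same day.

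**The concern.** Without a comparison group, a pre/post difference mixes any effect of acupuncture with everything else that changes over the two-month course. The protocol points to several such sources. Women may enter from 3 months after their last taxane. Other medication is allowed, and Sections 7.1 and 10 call it a potential confounder, but Section 12 contains no analysis of it. Section 7.4 drops women with fewer than 8 sessions, so the women analysed may differ from those enrolled.

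CIPN-20 has a further problem. If the score that qualified a woman also serves as her 'before' value, part of any later fall is regression to the mean. That bias favours acupuncture even if it does nothing.

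At stake is what may be concluded from the secondary analysis. As worded, the objective invites a causal answer that the tests cannot give.

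**Working it through.** The plan contains no power or effect-size calculation to reproduce; N = 20 is set by budget. The steps below size the problem.

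**1. Objective against analysis.** The lead sentence of 1.2 asks about impact, 1.2.2 asks about change, and the planned tests are within-group. The tests can answer 1.2.2 but not the lead sentence.

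**2. Where the cut-off sits.** The sensory subscale in Appendix A has 9 items scored 1 to 4, so the raw range is 9 to 36. Rescaled to 0-100, a raw 14 is (14 − 9)/27 × 100 = 18.5 and a raw 15 is 22.2. Entry therefore needs a raw score of 15 or more, which is low on the scale.

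**3. Regression to the mean if the selecting score is the 'before' value.** Assumptions, none of them in the documents: normal scores, SD 20, screened mean 30 to 40, test-retest correlation r of 0.7 to 0.9, no effect of AT and no untreated change.

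Expected fall = (1 − r) × SD × φ(z)/(1 − Φ(z)), with z = (20 − mean)/20.

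| Screened mean | z | φ(z)/(1 − Φ(z)) | r = 0.9 | r = 0.8 | r = 0.7 |
|---|---|---|---|---|---|
| 40 | −1.0 | 0.288 | 0.6 | 1.2 | 1.7 |
| 30 | −0.5 | 0.509 | 1.0 | 2.0 | 3.1 |
| 20 | 0 | 0.798 | 1.6 | 3.2 | 4.8 |

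The plausible range is about 0.6 to 3 points. The last row shows how it grows if the screened mean lies at the cut-off.

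**4. What this does to the test.** In a simulation of the paired t-test under the same assumptions (means 30 to 40, 20,000 runs per setting), a significant improvement appears in about 4.5% to 13% of null trials at n = 20. At n = 14, which is 70% of 20 and so the retention target, the range is about 4% to 10%. The nominal rate in that direction is 2.5%.

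**5. Multiplicity.** One before/after test per questionnaire at .05 gives 1 − 0.95⁴ = 18.5% for at least one false positive, if the four are independent. Correlation between questionnaires in the same women would usually lower this. These errors can fall in either direction, so this figure is separate from the bias in step 3.

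**6. Precision of a descriptive report.** The half-width of the 95% CI for mean change is t/√n in units of the SD of change: 2.093/√20 = 0.47 at n = 20 and 2.160/√14 = 0.58 at n = 14.

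**The case against.** The best defence is that 1.2.2 already asks only about change, that all primary endpoints are feasibility, and that a later randomised trial is the stated goal (Section 2). The protocol contains no rule that a p-value below .05 will be declared an effect. Section 10 already lists CIPN-20 at baseline, so the regression argument holds only if the calendar is followed. Much of this stands, and it keeps the point small. It does not remove it: 1.2.2 sits under the impact sentence, nothing disclaims attribution, and the calendar and Section 10 disagree on which score is the 'before' value.

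A reader might infer more than the documents support:

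- **That women are selected for high scores.** The floor is 20 of 100. Regression to the mean is small if most referred women score well above it.
- **That women are enrolled during natural recovery.** The only support is the Section 2 statement "40% of whom have persistent neuropathy after termination of chemotherapy", which gives no rate or timing of recovery. Entry requires current symptoms and has no upper limit on time since taxane, so stable chronic neuropathy fits equally well.
- **That the bias could reach 7 points.** With SD 20 and r = 0.7 this needs a screened mean of 10. That normal model puts 31% of scores below 0, which the scale does not allow, and it fits poorly with referral of women already diagnosed with CIPN.
- **That the false-positive chance is 51%.** This takes 14 independent tests (1 − 0.95¹⁴). Section 12 names four questionnaires, not seven scale scores, and the same scales at two follow-up times in the same women are not independent.
- **That an inflated effect will size the later trial.** No section says so. Section 2 describes the groundwork as showing that the team and location are in place.

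**Conclusion.** The point holds as a minor one. The lead sentence of Section 1.2 asks a causal question that a single-arm pre/post test cannot answer, and the protocol does not say that attribution will be withheld. If the calendar governs, CIPN-20 change also carries a bias towards improvement of about 0.6 to 3 points on 0-100. This rests on the assumed SD of 20, screened mean of 30 to 40 and correlation of 0.7 to 0.9, and would be larger if most screened women score near or below the cut-off. Untreated improvement may add to it, but the documents give no rate, so no figure is put on it. The 18.5% for four tests assumes independence. Recruitment, retention, safety and questionnaire-completion endpoints are not affected.

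**What to change.** 1. Reword the lead sentence of Section 1.2 to match 1.2.2, for example: describe change in reported CIPN from before to after AT.
2. In the Study Summary, where the .05 level stands, and in Section 12, replace significance claims with mean change, SD and 95% CI. State that no effect of AT will be inferred.
3. Reconcile the Section 9 calendar with Section 10 so that the CIPN-20 taken at the baseline visit is the 'before' value whenever screening was on an earlier day. Note in the text that regression to the mean remains when both visits fall on the same day.

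The cost is a weaker claim and, for women with separate visits, one short questionnaire repeated. N does not change.
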